3.2.2. Multiplicity-adjusted Secondary Efficacy Endpoints

The key secondary efficacy endpoint for this study is:

- change from Baseline to Week 65 in cUHDRS total score

The other multiplicity-adjusted secondary efficacy endpoints for this study are to evaluate the efficacy of pridopidine 45 mg bid vs. placebo as measured by:

- the proportion of participants with improvement or no worsening in UHDRS-TFC at Week 65 (change from Baseline \geq 0 points) using responder analysis
- change from Baseline to Week 52 in UHDRS-TFC score
- change from Baseline to Week 78 in UHDRS-TFC score
- change from Baseline to Week 65 in Q-Motor [REDACTED]
[REDACTED]

- change from Baseline to Week 65 in UHDRS-TMS (defined as the sum of all UHDRS motor domains ratings)
- change from Baseline to Week 65 in SDMT score
- change from Baseline to Week 52 in UHDRS-TMS score
- proportion of participants with no change or improvement in CGI-C at Week 65

For responder analyses where there are fewer than 5 responders (overall between both treatment groups), the analyses will not be performed as too few responders will not allow for comparison of responders between treated and placebo participants.

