3.2.3. Non-multiplicity Adjusted Secondary Efficacy Endpoints

The non-multiplicity adjusted secondary efficacy endpoints (listed in Section 2) will evaluate the efficacy of pridopidine 45 mg bid vs. placebo, as measured by change from Baseline to post-baseline scheduled visits in UHDRS-TFC (total score and subscales), cUHDRS, UHDRS-TMS (total score and subscales), dystonia score for those participants with severe dystonia at Baseline (defined as UHDRS-TMS-dystonia score ≥ 4), SDMT, SWR, Q-Motor measurements [REDACTED] at Weeks [REDACTED]

26, 39, 52, 65 and 78, if not presented as primary or multiplicity-adjusted secondary endpoints.

The proportion of participants with response in cUHDRS, UHDRS-TMS, Q-Motor [REDACTED] [REDACTED], and CGI-C at Weeks 26, 39 (not for Q-Motor assessments), 52, 65 and 78, if not presented as primary and multiplicity-adjusted secondary endpoints, will also be evaluated as non-multiplicity adjusted secondary efficacy endpoints. The response in each endpoint is defined as follows:

- Improvement or no worsening in Q-Motor [REDACTED] with change from Baseline ≤ 0 at corresponding post-baseline visit
- Improvement or no worsening in UHDRS-TMS with change from Baseline ≤ 0 at corresponding post-baseline visits
- Change from Baseline in cUHDRS ≥ -1 at corresponding post-baseline visits
- Response in CGI-C defined using different thresholds (i.e., 1, 1 to 2, 1 to 3, 1 to 4) at corresponding post-baseline visits

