7.4.2. UHDRS-TFC Response as a Binary Endpoint

The binary UHDRS-TFC response (yes or no) is defined as achieving improvement or no worsening in UHDRS-TFC score, i.e., change from Baseline to Week 65 in UHDRS-TFC ≥ 0

points. The responder analysis will be performed for the proportion of participants with change from baseline to Week 65 in UHDRS-TFC ≥ 0 .

The hypothesis testing to compare the percentage of responders between the two treatment groups will be based upon the mITT population. Logistic regression will be used to analyze and compare the probability of whether a participant is a UHDRS-TFC responder or not. The model will adjust for Baseline UHDRS-TFC, region, Baseline randomization stratification factors of neuroleptic use (Yes/No) and HD stage (HD1 and HD2).

The hypothesis testing of the UHDRS-TFC responder analysis is based on the main estimand as follows:

- Treatment: Pridopidine 45 mg bid or placebo (on background of standard of care) that participants are randomized to
- Population: Early HD Participants (HD1 & HD2) defined through the study inclusion/exclusion criteria. The mITT population will be used in analyzing this estimand
- Variable: Improvement or no worsening (change from Baseline ≥ 0 points) at Week 65 in UHDRS-TFC (Defined as responders to treatment)
- Population Level Summary: Proportion of responders, defined as the proportion of participants achieving improvement or no worsening in UHDRS-TFC (change from Baseline ≥ 0 points) at Week 65
- ICEs and Strategies for Addressing ICEs:

ICEs include treatment discontinuation and will be handled by combining composite strategy and hypothetical strategy as follows:

- Composite strategy: Observed UHDRS-TFC values will be used to determine if a participant is a responder or not. For treatment discontinuation due to disease-progression-related death, or meeting Stopping Rules, the participant will be considered a non-responder.
- Hypothetical strategy: For treatment discontinuation due to other reasons not included in composite strategy and no TFC data collected afterward, all values after ICEs will be imputed under MAR as if the participants had continued receiving the study treatment. The MAR imputation model will include UHDRS-TFC as a continuous response variable as described in Section 7.2. The UHDRS-TFC response at Week 65 (change from Baseline in UHDRS-TFC ≥ 0) will then be derived using the imputed UHDRS-TFC score as well as the non-missing UHDRS-TFC scores.

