The odds ratio (OR) of treatment effect (pridopidine 45 mg bid vs placebo) along with a 2-sided 95% CI and p-value will be presented. An estimate of OR > 1 will indicate a beneficial treatment effect. Descriptive statistics and 95% CI using Clopper-Pearson will be provided for the observed proportions at each visit, along with the difference between treatment groups in the proportions and 95% normally approximated CI for the difference.

Following supportive estimands will be used to support the analysis of this secondary endpoint:

Supportive Estimand 1: similarly defined as the main estimand for UHDRS-TFC responder analysis, but with population changed to ITT population, and MNAR instead of MAR MI will be used under the hypothetical strategy.

Supportive Estimand 2: similarly defined as the main estimand for UHDRS-TFC responder analysis, but with population changed to ITT population.

Supportive Estimand 3: similarly defined as the main estimand for UHDRS-TFC responder analysis, but with ICE handling strategy changed to treatment policy strategy (using observed data without imputation).

Supportive Estimand 4: similarly defined as Supportive Estimand 3 for UHDRS-TFC responder analysis, but with population changed to W65PP population.

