7.4.3. Other Multiplicity Adjusted Secondary Efficacy Variable and Analysis

For continuous endpoints such as change from Baseline using observed data only, the main estimand will be similar to the non-EMA-Estimand for the primary endpoint, analyzed using the mITT population with treatment policy strategy to handle ICEs. An MMRM model as described in Section 7.2 for the primary endpoint will be used with Baseline value of the analyzed variable replacing Baseline UHDRS-TFC as a covariate. For the specified visits, the LSMs, SE of the estimates, p-values, and 2-sided 95% CIs will be provided for the within treatment group changes from Baseline and for the comparison of change from Baseline between pridopidine and placebo.

Supportive estimands for continuous endpoints will be similar to the EMA-Estimand for the primary endpoint, with population as the ITT population and missing values imputed using copy reference method under MNAR assumption. Additional missing value imputation approach under MAR assumption may be used as a sensitivity analysis.

For analysis of change from Baseline in UHDRS-TFC at Week 78, main analysis will include observed values at scheduled visits up to 78 weeks. A sensitivity analysis for Week 78 endpoints will be performed with assessments between Week 65 and 78 mapped to Week 78.

For positive response defined using values of continuous variables:

- Unless otherwise specified, where a decrease reflects disease progression, a responder will be defined as those with no change or improvement (change from Baseline ≥ 0)
- Unless otherwise specified, where an increase in score reflects disease progression, a responder will be defined as those with change from Baseline ≤ 0

Main estimands for binary endpoints will be similar to the main estimand for the binary UHDRS-TFC response, analyzed in the mITT population and with ICEs handled by a combined composite and hypothetical strategy. Supportive estimand for the binary endpoints will be similar to Supportive Estimand 1 for the binary UHDRS-TFC response. All responder analyses or analyses of binary variables will be performed using logistic regression as indicated for the binary secondary variable above in Section 7.4.1.

The p-values from the main estimand will be used in the hierarchical testing for multiplicity adjusted secondary endpoints following the order described in Section 3.2.2.

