7.5. Non-Multiplicity Adjusted Secondary Efficacy Variable and Analysis

Other non-multiplicity adjusted secondary efficacy variables are listed and defined in Sections 2 and 3.2.3.

For all Q-Motor analyses [REDACTED]

[REDACTED] Analysis of Q-Motor [REDACTED]

For continuous variables, an MMRM model as described in Section 7.2 for the primary endpoint in mITT population will be used, with Baseline value of the analyzed variable replacing Baseline UHDRS-TFC as a covariate. For the specified visits, the LSMs, SE of the estimates, p-values, and 2-sided 95% CIs will be provided for the within treatment group changes from Baseline and for the comparison of change from Baseline between pridopidine and placebo. This will be repeated in W65PP or W78PP population depending on whether change to Week 65 or 78 is analyzed.

In addition, actual values and changes from Baseline to each visit will be summarized using descriptive statistics for each endpoint. The sub-scale scores of each endpoint will also be summarized where applicable.

The proportion of responders will be analyzed in a similar way to how the binary UHDRS-TFC response is analyzed for the main estimand and Supportive Estimand 1. Different thresholds than specified above may be explored. Descriptive statistics and 95% CI using normal approximation will be provided for the proportions at each visit. In order to minimize impact of outliers that may represent unrealistic changes in key endpoints, analyses using robust regression or other methods may be performed.

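### The five-responder cut-off pools both arms, so a logistic analysis can still run with no responders in one arm; a default fit then gives no finite odds ratio and a Wald p near 1

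*SAP*

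**What the plan says.** SAP 3.2.2 gives the only rule on sparse responder data: "For responder analyses where there are fewer than 5 responders (overall between both treatment groups), the analyses will not be performed". Its stated reason is that so few responders do not permit a comparison of the arms. The SAP version history shows that the rule came in with version 3.0.

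Above that count, SAP 7.4.2 applies: "Logistic regression will be used to analyze and compare the probability of whether a participant is a UHDRS-TFC responder or not". The model adjusts for Baseline TFC, region, neuroleptic use and HD stage. On output, "The odds ratio (OR) of treatment effect (pridopidine 45 mg bid vs placebo) along with a 2-sided 95% CI and p-value will be presented". The same section plans Clopper-Pearson intervals for the observed proportions and a normal-approximation interval for their difference.

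SAP 7.4.3 extends the model: "All responder analyses or analyses of binary variables will be performed using logistic regression". SAP 7.5 covers the endpoints outside the hierarchy: "The proportion of responders will be analyzed in a similar way to how the binary UHDRS-TFC response is analyzed for the main estimand". Those endpoints include "Response in CGI-C defined using different thresholds (i.e., 1, 1 to 2, 1 to 3, 1 to 4) at corresponding post-baseline visits" (SAP 3.2.3), at Weeks 26, 39, 52, 65 and 78.

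Neither document gives a minimum per arm, a rule for an empty cell, a minimum for non-responders, or a sparse-data method such as Firth or exact logistic regression. Neither names the estimation method or test statistic for the logistic model.

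**The concern.** The cut-off is meant to stop comparisons that the data cannot support, but a pooled count does not identify them. If every responder is in one arm, the treatment term is separated from the outcome and the likelihood keeps rising as the log odds ratio grows. Software stops at an arbitrary large value with a far larger standard error, usually with a warning. The Wald statistic is then close to zero.

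The SAP names endpoints where this could happen. CGI-C score 1 (very much improved) and scores 1 to 2, each at five visits, make ten planned analyses in a disease that the protocol (8.1.1) describes as one of steady functional decline. For such an endpoint, the table could show an uninterpretable odds ratio and a p-value near 1 beside a one-sided split of counts.

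**Working it through.** **Inputs.** 240 per arm (SAP 3.1), two-sided 5% tests (SAP 5.4), pooled cut-off of 5 (SAP 3.2.2), covariates from SAP 7.4.2. The documents give no derivation of the cut-off to reproduce. The split 8 versus 0 is an illustration, and all response rates below are assumptions.

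**1. Does the rule stop it?** 8 + 0 = 8, which is at least 5, so the analysis runs.

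**2. Maximum-likelihood fit, 8/240 versus 0/240.** With usual convergence settings the log odds ratio stops at 17.84 with SE 2594.4.
- z = 17.84 / 2594.4 = 0.007, so Wald p = 0.9945.
- With the SAP covariates added (200 simulated covariate sets), the median Wald p is 0.994, range 0.994 to 0.996.
- Splits of 5, 6 and 10 versus 0 give Wald p between 0.991 and 0.995, at 240 or at 186 per arm.

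**3. Other tests on the same 8 versus 0.**
- Fisher's exact p = 0.0074.
- Likelihood ratio: 2 × (difference in log-likelihood) = 11.23 on 1 df, p = 0.0008.
- Firth odds ratio, unadjusted (equivalent here to adding 0.5 to each cell): (8.5/232.5) / (0.5/240.5) = 17.6. Penalised likelihood-ratio p = 0.003.

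**4. Planned interval for the difference.** 8/240 = 3.33%. SE = √(0.0333 × 0.9667 / 240) = 1.16 points. The 95% interval is 3.33 ± 1.96 × 1.16, or 1.1 to 5.6 points. It excludes zero, beside an odds-ratio p of 0.99.

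**5. Does multiple imputation cure it?** No. If one of 100 imputed datasets is separated, the average within-imputation variance is at least 2594²/100, so the pooled SE is about 259 and p is again about 0.99.

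**6. How often?** The chance of separation, given that the analysis runs, is P(0 in one arm) × P(at least 5 in the other) / P(total at least 5). Binomial, 240 per arm, placebo versus active; the reverse split adds almost nothing.
- 1.2% versus 3%: 0.0552 × 0.8485 / 0.9736 = 4.8%.
- 0.2% versus 3%: 0.6185 × 0.8485 / 0.8840 = 59%.
- No treatment effect: 6.1% if there are exactly 5 responders in total, 0.7% if there are 8.

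**7. Power, given that the analysis runs.** Unadjusted, by exact enumeration of the two binomials:

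| Rates | ML Wald | Fisher | Firth Wald | Firth penalised LR |
|---|---|---|---|---|
| 1.2% vs 3% | 15% | 18% | 17% | 25% |
| 0.2% vs 3% | 16% | 67% | 46% | 81% |

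**8. Which form of Firth?** Combining Firth estimates and SEs by Rubin's rules is again a Wald test. For 8 versus 0: ln 17.58 = 2.867, SE 1.461, z = 1.96, p = 0.050. For 5 versus 0, p = 0.10. The penalised likelihood-ratio values are 0.003 and 0.026. Simply switching on Firth within the imputed analysis therefore recovers only part of the loss.

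**The case against.** Four points on the other side have force.

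**The hierarchy.** Because the rule stands in the section on multiplicity-adjusted endpoints, a reader might infer that confirmatory conclusions are at risk. The documents do not support that. The two responder endpoints in the hierarchy are TFC change of at least 0 and CGI-C 1 to 4 at Week 65. Both count unchanged participants as responders, so an empty arm is implausible. This is a judgement, since no expected rates are given.

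**Other output.** A reader might also infer that the plan would report no difference exactly when the arms differ most. That goes too far. SAP 7.4.2 also plans the difference in proportions with its interval, and SAP 7.5 carries the approach over, so the artefact would be visible. What remains is that two planned outputs would contradict each other with no rule on which to believe. In addition, the normal-approximation interval that SAP 7.5 plans for each proportion has zero width at 0/240.

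**The test is inferred.** The SAP names neither maximum likelihood nor Wald, and the Rubin's-rule text in SAP 5.8.1.2 is written around the MMRM. A likelihood-ratio test on observed data would give 0.0008. This stands as a caveat, but it also shows how far the result depends on an unstated choice.

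**Frequency.** High separation rates need extreme contrasts. On a latent-normal scale, 0.2% versus 3% is a shift of 1.00 SD. The design effect is 0.7/1.9 = 0.37 SD (SAP 3.3), which with 3% on active implies about 1.2% on placebo. Separation is then about 5%, and ML Wald and Fisher differ little in power. This stands, and it limits the weight of the point.

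**Conclusion.** The point holds, within narrow limits. The cut-off does not screen out the case in which one arm is empty, and the SAP gives no method for it. An ordinary fit then has no finite odds ratio and a Wald p near 1, where Fisher gives 0.007 at 8 versus 0.

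The exposure is the CGI-C thresholds 1 and 1 to 2, further exploratory thresholds (SAP 7.5) and small subgroups. No confirmatory test is expected to be affected.

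Two assumptions carry the conclusion: that the default maximum-likelihood and Wald route is used, and that responders are rare at these thresholds. The failure at a given one-sided split does not depend on response rates. How often such a split arises does, and the range of about 5% to 59% rests wholly on assumed rates.

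**What to change.** Keep the existing rule that the analysis is not performed with fewer than 5 responders in total, and add to SAP 3.2.2:

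> If either arm has fewer than 5 observed responders or fewer than 5 observed non-responders at the visit, the treatment comparison for that endpoint is based on observed cases, using the same logistic model with Firth's penalised likelihood (PROC LOGISTIC, FIRTH option). The profile penalised-likelihood CI and the penalised likelihood-ratio p-value are reported, with counts per arm and Fisher's exact p. If an imputed version is also shown, Firth is used in all 100 datasets and the result is labelled supportive, because its pooled test is a conservative Wald test.

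Tying the trigger to observed counts means that imputed datasets cannot fall on different sides of it, and using Firth in all 100 avoids pooling two kinds of estimate.

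The cost is a few sentences and one option in the software already specified. The downsides are slight shrinkage of the odds ratio and reliance on observed cases, in place of the imputed main estimand, for these rare-response endpoints. Under equal rates of 1.25% to 2%, the penalised likelihood-ratio test keeps its type I error at about 4% (same enumeration as above).

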3.2.3. Non-multiplicity Adjusted Secondary Efficacy Endpoints

The non-multiplicity adjusted secondary efficacy endpoints (listed in Section 2) will evaluate the efficacy of pridopidine 45 mg bid vs. placebo, as measured by change from Baseline to post-baseline scheduled visits in UHDRS-TFC (total score and subscales), cUHDRS, UHDRS-TMS (total score and subscales), dystonia score for those participants with severe dystonia at Baseline (defined as UHDRS-TMS-dystonia score ≥ 4), SDMT, SWR, Q-Motor measurements [REDACTED] at Weeks [REDACTED]

26, 39, 52, 65 and 78, if not presented as primary or multiplicity-adjusted secondary endpoints.

The proportion of participants with response in cUHDRS, UHDRS-TMS, Q-Motor [REDACTED] [REDACTED], and CGI-C at Weeks 26, 39 (not for Q-Motor assessments), 52, 65 and 78, if not presented as primary and multiplicity-adjusted secondary endpoints, will also be evaluated as non-multiplicity adjusted secondary efficacy endpoints. The response in each endpoint is defined as follows:

- Improvement or no worsening in Q-Motor [REDACTED] with change from Baseline ≤ 0 at corresponding post-baseline visit
- Improvement or no worsening in UHDRS-TMS with change from Baseline ≤ 0 at corresponding post-baseline visits
- Change from Baseline in cUHDRS ≥ -1 at corresponding post-baseline visits
- Response in CGI-C defined using different thresholds (i.e., 1, 1 to 2, 1 to 3, 1 to 4) at corresponding post-baseline visits

3.2.4. Other Exploratory Efficacy Endpoints

The other exploratory efficacy endpoints for this study are to evaluate the efficacy of pridopidine 45 mg bid vs. placebo as assessed by:

- Problem Behaviors assessment, as assessed by the change from Baseline to Weeks 26, 52, 65 and 78 in PBA-s total score
- Change from Baseline to Weeks 26, 52, 65 and 78 in PBA-s apathy sub-scores
- Change from Baseline to Weeks 26, 52, 65 and 78 in HDQoL

3.2.5. Biomarker Endpoints

- Evaluate the efficacy of pridopidine 45 mg bid vs. placebo as assessed by the change from Baseline to Weeks 26, 52, 65 and 78 in plasma NfL protein
- Evaluate the relationship between Baseline NfL and changes from Baseline in select efficacy endpoints
- Evaluate the relationship between changes from Baseline to Weeks 26, 52, 65 and 78 in plasma NfL and select efficacy endpoints for pridopidine 45 mg bid vs. placebo
- Proportion of participants with stabilization or improvement in change from Baseline to Week 26, 52, 65 and 78 in plasma NfL levels

3.2.6. Pharmacokinetic Endpoints

- To evaluate plasma concentration of pridopidine and its main metabolite at Weeks 26, 52, 65, and 78. For Week 78 analysis include participants' who had their EoS visit between Week 65 and 78.
- To study the relationship between plasma concentration of pridopidine and clinical outcomes including change from Baseline in UHDRS-TFC, UHDRS-TMS, Q-Motor, cUHDRS, SDMT, and SWR.

3.2.7. Safety Endpoints

Safety endpoints will include the following:

- Incidence of AEs and SAEs throughout the study
- Changes from Baseline and absolute thresholds as per ICH E14 in QTcF and other ECG parameter assessments throughout the study
- Change in clinical safety laboratory tests (serum/blood chemistry, hematology, and urinalysis) and summary of abnormalities throughout the study
- Changes from Baseline C-SSRS throughout the study
- Change in vital signs and summary of abnormalities throughout the study
- Abnormalities in Physical Exam
- Abnormalities in Neurological Exam

3.2.8. Tolerability Endpoints

Tolerability endpoints will include the following:

- The number (%) of participants who complete the treatment period on study drug
- The number (%) of participants who failed to complete the treatment period on study drug due to an AE
- The number (%) of participants who fail to complete the treatment period due to QTcF, CrCl or Psychiatric Stopping Rules

3.3. Sample Size and Power Considerations

Based on experience with early HD participants in the prior Phase 2 PRIDE-HD study, we expect the difference in mean change from Baseline to Week 65 between the 45 mg bid treated and placebo groups to be 0.7 points on the UHDRS-TFC with a standard deviation (SD) of 1.9 points.

A total sample size of 372 participants will provide 94% power to detect a between-group difference of 0.7 points in the mean change from Baseline to 65 weeks in the UHDRS-TFC score, with an SD of 1.9 points, using a two-tailed t-test at a significance level of 0.05. Assuming a drop-out rate of 22.5%, a total of 480 participants will be randomized. The sample size was calculated using SAS version 9.4 PROC POWER.

Based on feedback from Regulatory Authorities, the power assessment was updated as below. Assuming a dropout rate of 22.5 % in each treatment group early in the study, under assumption of Missing Not at Random (MNAR) with imputed values for all discontinued participants estimated based on the trajectory of placebo participants with available data, we anticipate a difference in change from Baseline to imputed values at Week 65 for this group to be 0.1 points. The overall difference would then be 0.565 (0.7*0.775+0.1*0.225) or 0.7 points for the 77.5% completers and 0.1 points for the 22.5 % participants who discontinue and have imputed data at Week 65. A difference of 0.565 points with SD of 1.9 with a sample size of 480 participants would provide 90% power (SAS V 9.4 PROC POWER).

